**Principal Investigator:**

**[name]**

**Sponsor:**

**The Republican Research and Practical Center for Epidemiology and Microbiology**

**Document Date:**

**June 06, 2024**

## **Collection of peripheral blood for the study**

We collected 5-10 ml of venous blood under aseptic conditions into two tubes. One tube with anticoagulant (heparin solution or ethylenediaminetetraacetate (EDTA)), the second tube with blood coagulation activator. The closed vacutainer with blood is inverted several times to mix the blood with the anticoagulant. The patient's blood was delivered to the Immunology and Cell Biotechnology Laboratory within no more than 4 hours of collection.

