## **Investigation of cellular immunity indicators**

Sample preparation includes the following steps

- Spreading of antibodies according to the developed panel in test tubes;
- Adding 100 µl of blood to the antibody mixture and mixing thoroughly;
- Incubation for 15 min at +4 - +12°C in the dark;
- Add 2 ml of lysis solution to lyse the erythrocytes, mix the tube contents;
- Incubate for 10 minutes at +16 to +30°C in the dark;
- Centrifuge the tubes (200-300 g - 5 minutes) to precipitate the leucocytes;
- Add 150 µl DPBS and mix.
- Count on a flow cytometer.

Counting of cell samples on a FACSCalibur cytofluorimeter included the following mandatory steps

- Performance control/calibration of the instrument;
- Adjustment of light scattering parameters on the cytogram plotted in FSC\SSC coordinates;
- adjustment of the 'threshold' parameters on the FSC channel to exclude cell debris from the analysis;
- Adjusting the voltage on the fluorescence channels using an unstained control sample;
- Adjusting the spectral compensation using single stain controls;
- Counting of the test sample at 50,000 leukocytes.

Data were analysed using Flowing Software version 2.5.1 or BD FACSDiva 7.0.

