## **Sample Preparation for the Study of Spontaneous and Stimulated Production of Oxygen Radicals (ROS) by Blood Neutrophils**

Sample preparation involves the following steps:

- Labelling (positive '+' - stimulated sample and negative '-' - unstimulated sample) and serial numbering of sample tubes;
- Place the cytometer tubes in a rack and number them;
- Add 1 µl of DHR to the tubes;
- Add 50 µl of RPMI medium;
- Add 50 µl of blood and mix thoroughly;
- Incubate for 10 minutes at +37°C;
- Add 20 µl RPMI to '+' samples only and mix the contents of the tube;
- Incubate for 30 min at +37°C in the thermostat;
- Add 2 ml lysis solution, mix tube contents;
- Incubate for 10 min at +16 - +30°C in the dark;
- Centrifuge the tubes (200-300 g - 5 minutes) to precipitate the leucocytes;
- Add 100 µl DPBS and mix.

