## **Sample preparation for the spontaneous necrosis and apoptosis of peripheral blood cells (PI, Annexin V FITC) assay.**

Sample preparation involves the following steps:

- Appropriately label two tubes (stained and unstained sample) for the cytometer;
- Prepare a 1X lysis solution by diluting a 10X stock solution;
- Prepare a single annexin binding buffer by diluting the 10x stock solution;
- Add 1 ml of blood to a 15 ml tube;
- adding 14 ml of lysing solution to the tube containing blood, mixing the contents of the tube;
- Incubate for 10 minutes at room temperature in the dark;
- Centrifuge the tubes (200-300g - 5 minutes) to precipitate the leucocytes;
- Wash the precipitate with 2.5 ml DPBS: add 2.5 ml DPBS, tip to resuspend the cells;
- Centrifuge the tubes (200-300g - 5 minutes) to precipitate the cells;

- Collect the supernatant;
- Dissolve the precipitate in 200 µl of cold single annexin binding buffer;
- Transfer 100 µl of cell suspension to two cytometer tubes;
- diluting the volume of the cell suspension to 500 µl with cold single annexin-binding buffer;
- adding 2.5 µl Annexin V FITC and 2.5 µl PI only to the stained sample tube;
- gentle stirring on a vortex;
- incubation at room temperature for 20 min in a dark place.
- counting on a flow cytometer.

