### **Statistical processing of results**

Statistical processing of the data obtained was performed using Statistica version 12 (StatSoft, USA). Values are presented as Me (25 - 75), where Me is the median and 25 and 75 are the interquartile ranges as 25th and 75th percentiles. The normality of the distribution of values was assessed using the Shapiro-Wilk W criterion. Given the lack of normal distribution in the samples studied, non-parametric methods were used to compare groups of data and study correlations. The Mann-Whitney U-criterion was used to compare two independent samples. A significance level of  $p < 0.05$  was used as the criterion for reliability of differences between indicators.

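### Does leaving the anticoagulant open (heparin or EDTA) call for a change to the plan?

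*Combined protocol and SAP*

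**What the plan says.** The section on collection of peripheral blood states the draw and the tubes in the past tense: "We collected 5-10 ml of venous blood under aseptic conditions into two tubes". It continues: "One tube with anticoagulant (heparin solution or ethylenediaminetetraacetate (EDTA)), the second tube with blood coagulation activator". The only later reference to the additive is generic and does not settle which it was: "The closed vacutainer with blood is inverted several times to mix the blood with the anticoagulant".

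Each of the three assay sections then starts from blood without naming a collection tube:

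- **Cellular immunity indicators:** 100 µl "of blood to the antibody mixture and mixing thoroughly".
- **Oxygen radicals in neutrophils:** 50 µl "of blood and mix thoroughly", in a stimulated and an unstimulated tube.
- **Necrosis and apoptosis:** "Add 1 ml of blood to a 15 ml tube", later divided between a stained and an unstained tube.

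The statistics section gives the comparison: "The Mann-Whitney U-criterion was used to compare two independent samples". It mentions no stratification or adjustment for sample handling.

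**The concern.** The wording permits two different additives in the tube that appears to feed every cellular measurement, and it never says which was chosen. If the choice varied from one participant to the next, the material under study would differ between people, and the planned rank test compares people. If the choice also went along with group membership, and the two additives gave different readings, part of any group difference could belong to the tube. The test has no term that would separate the two, and a reader would have no counts by group to check. A laboratory wishing to repeat the work would also not know which of the two permitted options to copy.

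**Working it through.** The plan gives no figure on this point to reproduce. The check is whether the text resolves the choice, whether one tube can feed all three assays, and what would have to be true for a result to be wrong.

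**1. Is the choice resolved anywhere?** No. From the blood-collection section to the statistics section, the additive is named once, as either of two, and mentioned once more without a name. The omission is real.

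**2. Could the two options refer to different assays?** Only one anticoagulated tube is described; the other contains a clotting activator. All three assays pipette liquid blood, lyse the red cells and recover leucocytes, so the anticoagulated tube is the natural source. No sentence says so, and this is an inference. The volumes fit it:

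- Cellular immunity, one antibody tube: 0.1 ml
- Oxygen radicals, two tubes: 2 × 0.05 = 0.1 ml
- Necrosis and apoptosis: 1.0 ml
- Total: 0.1 + 0.1 + 1.0 = **1.2 ml**

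The number of antibody tubes is not stated. With eight, the total is 0.8 + 0.1 + 1.0 = **1.9 ml**. If the draw is split equally (an assumption), the anticoagulated tube holds 5/2 = 2.5 ml to 10/2 = 5 ml. Even the smaller tube is enough.

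A participant who had all three assays would therefore have one type for all of them. Two readings remain: one type for everyone, or a type that varies between participants. The text does not choose between them.

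**3. What would make a result wrong?** On this reading, the stimulated and unstimulated tubes of one participant share an anticoagulant, as do the stained and unstained tubes. The type could vary only between participants, and distortion of the Mann-Whitney comparison would then need three things together:

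| Condition | Support in the documents |
|---|---|
| Both types were actually used | None; the wording only permits either |
| The mix differed between the groups compared | None; neither the groups nor the tube counts are given |
| The type shifts a measured value | None; no section says so |

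If the first fails, there is nothing to compare. If the second fails, so that type is unrelated to group, the rank test keeps its error rate and at worst loses some power to extra spread. If the third fails, the type is irrelevant to the result.

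**4. Do the stated volumes show an effect?** In the oxygen-radical assay, blood is diluted with 1 µl of dye and 50 µl of medium, so the anticoagulant is at 50/(1 + 50 + 50) = 49.5% of its collection-tube concentration. After the further 20 µl added to the stimulated tube it is at 50/(1 + 50 + 50 + 20) = 41.3%. This shows that the additive is still present during incubation. It does not show that heparin and EDTA give different readings, and the documents offer no threshold against which to judge the percentages. Nor does dilution at the assay measure total exposure, since up to 4 hours may pass between collection and delivery to the laboratory.

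**The case for a change.** The strongest argument for acting is that it costs almost nothing. The blood has been collected, the answer should be known, and one sentence would settle it. The comparison is between participants, which is the level at which one anticoagulated tube per person lets the type vary, and blood goes unwashed into both the antibody staining and the 37°C incubation. If both types were used and recorded, counts by group and a rank comparison stratified by tube type could be shown beside the planned test.

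Part of this stands. The omission is genuine, and naming the reagent would help anyone repeating the method. The rest depends on facts that the documents do not show. A stratified test has a purpose only if both types were used and the type was recorded, and there is no sign of either. Asking for the type assay by assay would also sit badly with the description of a single anticoagulated tube. For samples already drawn, no instruction in the plan can alter what they were collected in. The sampling is also not beyond repetition: volume, tube kinds, permitted additives and the delivery limit are all given, and only the choice within a stated pair is open.

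**Conclusion.** No change to the plan follows. This is missing reagent detail of a kind that the laboratory can supply from its own records, not a fault in the design or in the analysis. The size of any effect on results cannot be computed, because sample size, groups, tube mix and any tube effect are all absent from the documents; no bias and no error rate is claimed. Naming the anticoagulant in the results report, and saying whether it was the same for all participants and groups, would be good practice. If both turn out to have been used, a count by group, or a statement that the type was not recorded, would be enough.

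The conclusion rests on two assumptions: that the anticoagulated tube supplied all three assays, which is inferred from the use of liquid blood, and that the sections on collection, assays and statistics contain everything the plan says on the matter. It would need another look only if records showed that both types were used in different proportions between the groups compared.

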## **Investigation of cellular immunity indicators**

Sample preparation includes the following steps

- Spreading of antibodies according to the developed panel in test tubes;
- Adding 100 µl of blood to the antibody mixture and mixing thoroughly;
- Incubation for 15 min at +4 - +12°C in the dark;
- Add 2 ml of lysis solution to lyse the erythrocytes, mix the tube contents;
- Incubate for 10 minutes at +16 to +30°C in the dark;
- Centrifuge the tubes (200-300 g - 5 minutes) to precipitate the leucocytes;
- Add 150 µl DPBS and mix.
- Count on a flow cytometer.

Counting of cell samples on a FACSCalibur cytofluorimeter included the following mandatory steps

- Performance control/calibration of the instrument;
- Adjustment of light scattering parameters on the cytogram plotted in FSC\SSC coordinates;
- adjustment of the 'threshold' parameters on the FSC channel to exclude cell debris from the analysis;
- Adjusting the voltage on the fluorescence channels using an unstained control sample;
- Adjusting the spectral compensation using single stain controls;
- Counting of the test sample at 50,000 leukocytes.

Data were analysed using Flowing Software version 2.5.1 or BD FACSDiva 7.0.

## **Sample Preparation for the Study of Spontaneous and Stimulated Production of Oxygen Radicals (ROS) by Blood Neutrophils**

Sample preparation involves the following steps:

- Labelling (positive '+' - stimulated sample and negative '-' - unstimulated sample) and serial numbering of sample tubes;
- Place the cytometer tubes in a rack and number them;
- Add 1 µl of DHR to the tubes;
- Add 50 µl of RPMI medium;
- Add 50 µl of blood and mix thoroughly;
- Incubate for 10 minutes at +37°C;
- Add 20 µl RPMI to '+' samples only and mix the contents of the tube;
- Incubate for 30 min at +37°C in the thermostat;
- Add 2 ml lysis solution, mix tube contents;
- Incubate for 10 min at +16 - +30°C in the dark;
- Centrifuge the tubes (200-300 g - 5 minutes) to precipitate the leucocytes;
- Add 100 µl DPBS and mix.

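### The stimulated tube in the neutrophil ROS assay receives only more RPMI, and the document names no stimulant

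*Combined protocol and SAP*

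**What the plan says.** The heading of the assay section announces "Spontaneous and Stimulated Production of Oxygen Radicals (ROS) by Blood Neutrophils", so two measurements are intended.

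The first step fixes the labels: "Labelling (positive '+' - stimulated sample and negative '-' - unstimulated sample) and serial numbering of sample tubes".

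Three additions follow with no tube restriction: 1 µl "of DHR to the tubes", 50 µl "of RPMI medium", and 50 µl of blood. The tubes are then incubated for 10 minutes at +37°C.

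Next comes the one step confined to the '+' tubes, 20 µl of "RPMI to '+' samples only and mix the contents of the tube". A 30 min incubation at +37°C follows. Lysis with 2 ml of solution, a further incubation, centrifugation and 100 µl of DPBS are again unrestricted.

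The section on statistical processing does not mention ROS. It says in general terms that "non-parametric methods were used to compare groups of data and study correlations".

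**The concern.** A tube labelled stimulated must receive something that stimulates. The only thing that sets it apart here is an extra volume of a medium that both tubes already hold. The label and the procedure therefore contradict each other.

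Stimulated production is one of the two quantities the assay exists to measure. If the steps were carried out as written, a comparison of '+' with '-' sets unstimulated blood against unstimulated blood that was somewhat more dilute during one incubation, and any value reported as stimulated is mislabelled. If a stimulant was in fact used, the reader cannot learn which one or at what concentration, so the result can be neither interpreted nor repeated.

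**Working it through.** The document states no figure to reproduce for this point. The check is a reading of the steps by tube, a search for a stimulant, and a sum of volumes.

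**1. Steps by tube (ROS sample preparation section)**

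| Step | '-' tube | '+' tube |
|---|---|---|
| DHR | 1 µl | 1 µl |
| RPMI | 50 µl | 50 µl |
| Blood | 50 µl | 50 µl |
| 10 min at +37°C | yes | yes |
| Further RPMI | none | 20 µl |
| 30 min at +37°C | yes | yes |
| Lysis solution | 2 ml | 2 ml |
| DPBS after centrifugation | 100 µl | 100 µl |

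That both tubes receive the 50 µl of RPMI is an inference from the lack of a restriction in that step. It is the natural reading, because the later step says explicitly when a restriction is meant. If it were wrong, RPMI would still be the only '+'-specific addition and no stimulant would be named.

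**2. Search for a stimulant.** Counting each item once at first mention, from the blood collection section to the statistical section:

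- Blood collection: heparin, EDTA, coagulation activator (3)
- Cellular immunity: antibodies, lysis solution, DPBS (3)
- ROS assay: DHR, RPMI (2)
- Necrosis and apoptosis assay: annexin binding buffer, Annexin V FITC, PI (3)
- Statistical processing: none (0)

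The total is 3 + 3 + 2 + 3 + 0 = 11, and none of the 11 is described as a neutrophil stimulant. The only activator mentioned is the additive in "the second tube with blood coagulation activator". It belongs to blood collection and appears in no step of the ROS assay.

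**3. Tube contents during the 30 min incubation, as written**

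- '-' tube: 1 + 50 + 50 = 101 µl
- '+' tube: 101 + 20 = 121 µl

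| Component | '-' | '+' |
|---|---|---|
| Blood | 50/101 = 49.5% | 50/121 = 41.3% |
| RPMI | 50/101 = 49.5% | 70/121 = 57.9% |
| DHR | 1/101 = 0.99% | 1/121 = 0.83% |

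Relative fall in blood and DHR concentration in '+': 1 − 101/121 = 16.5%.

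**4. After lysis solution is added.** The volumes become 101 + 2,000 = 2,101 µl and 121 + 2,000 = 2,121 µl, a relative difference of 1 − 2,101/2,121 = 0.9%. The written difference between the tubes is therefore material only during the 30 min incubation. The amount of blood is the same in both tubes throughout.

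**The case against.** The strongest reply is that this is a writing slip: the laboratory used a stimulant, perhaps one carried in RPMI, and its name was dropped. On that view the percentages above describe a tube nobody prepared, and the point shrinks to one unnamed reagent. This is plausible, and the document cannot rule it out. It does not remove the need for correction, since the agent and concentration would then be missing. No matching 20 µl addition to the '-' tube is listed either, so the volume difference would still need explaining.

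A second reply is that, even read literally, the dilution is brief. That stands: the tubes have equal volumes in the first incubation, and the difference all but vanishes once lysis solution is added. No effect of the dilution on the ROS signal has been shown, and none is claimed.

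A third is that the reagent count depends on choices, such as counting heparin and EDTA separately although they are alternatives. That is fair. The finding needs only the statement that no stimulant is named, and no way of counting changes it.

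A fourth is that the paired cytometry readings could themselves show whether stimulation took place. A clear shift between the tubes might suggest that something active was added. It would not identify the agent or its concentration, so the result still could not be interpreted or reproduced as a defined stimulated measurement.

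Finally, much of the document describes completed work, so this is a correction of reporting and not of design. That is right, and it limits the severity.

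**Conclusion.** The concern holds. The '+' tube is defined as stimulated, its only specific addition is 20 µl of RPMI, and no stimulant is named in the available text. The step reads as a complete instruction, with no redaction mark or gap. As written, the only difference between the tubes is that blood and DHR are 16.5% more dilute in '+' during the 30 min incubation.

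Confidence is high about what the text says. What the laboratory did is unknown. The conclusion rests on reading the unrestricted steps as applying to both tubes, and on the sections available for review.

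This should be fixed, but its reach is limited. It affects the validity of the stimulated label and the reproducibility of one arm of one assay. The text ties no endpoint to ROS, and no consequence for the Mann-Whitney comparison is asserted.

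**What to change.** Check the laboratory records for what was added to the '+' tubes and what, if anything, was added to the '-' tubes at the same point. Then correct the step from those records, in a form such as: *Add [volume as recorded] of [stimulating agent as recorded] at [concentration as recorded] to the '+' tubes; [addition to the '-' tubes as recorded, or none].* No agent, volume or concentration is proposed here; these must come from the records.

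If the records show that only RPMI was added, or cannot show that a stimulant was used, do not report or interpret the '+' values as stimulated ROS.

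The cost is one records check and one corrected line, with no extra patients, visits or blood. The downside is that the stimulated ROS result is lost if the records show only RPMI or are silent.

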## **Sample preparation for the spontaneous necrosis and apoptosis of peripheral blood cells (PI, Annexin V FITC) assay.**

Sample preparation involves the following steps:

- Appropriately label two tubes (stained and unstained sample) for the cytometer;
- Prepare a 1X lysis solution by diluting a 10X stock solution;
- Prepare a single annexin binding buffer by diluting the 10x stock solution;
- Add 1 ml of blood to a 15 ml tube;
- adding 14 ml of lysing solution to the tube containing blood, mixing the contents of the tube;
- Incubate for 10 minutes at room temperature in the dark;
- Centrifuge the tubes (200-300g - 5 minutes) to precipitate the leucocytes;
- Wash the precipitate with 2.5 ml DPBS: add 2.5 ml DPBS, tip to resuspend the cells;
- Centrifuge the tubes (200-300g - 5 minutes) to precipitate the cells;

- Collect the supernatant;
- Dissolve the precipitate in 200 µl of cold single annexin binding buffer;
- Transfer 100 µl of cell suspension to two cytometer tubes;
- diluting the volume of the cell suspension to 500 µl with cold single annexin-binding buffer;
- adding 2.5 µl Annexin V FITC and 2.5 µl PI only to the stained sample tube;
- gentle stirring on a vortex;
- incubation at room temperature for 20 min in a dark place.
- counting on a flow cytometer.

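### Does the Annexin V/PI assay need written population definitions and its own compensation step?

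*Combined protocol and SAP*

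**What the plan says.** The heading of the assay section names two processes and two dyes: "Sample preparation for the spontaneous necrosis and apoptosis of peripheral blood cells (PI, Annexin V FITC) assay". The steps prepare two tubes ("Appropriately label two tubes (stained and unstained sample) for the cytometer"), put both dyes into one of them ("adding 2.5 µl Annexin V FITC and 2.5 µl PI only to the stained sample tube") and finish with "counting on a flow cytometer". The section defines no quadrants or populations and does not refer to any other section.

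The instructions for running the cytometer are under *Investigation of cellular immunity indicators*. A list presented as compulsory for counting cell samples on the named instrument includes calibration, light-scatter settings, a threshold against debris, voltage setting on an unstained control, "Adjusting the spectral compensation using single stain controls" and "Counting of the test sample at 50,000 leukocytes". The same section adds "Data were analysed using Flowing Software version 2.5.1 or BD FACSDiva 7.0".

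*Statistical processing of results* provides medians with quartiles and a two-group test: "The Mann-Whitney U-criterion was used to compare two independent samples". It does not mention how cell populations are defined.

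**The concern.** Two dyes give three positive populations: Annexin V only, both dyes, and PI only. The heading names two processes. Double-positive cells can be reported as late apoptosis, as necrosis, or on their own, so one data file can yield different values for apoptosis and necrosis. Two analysis programs are allowed, and no common rule links them.

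Compensation raises a second doubt. The assay lists one unstained tube and one tube with both dyes, and neither is a single-stain control. The compensation step sits under a different heading. If it were skipped, FITC signal in the PI channel could make some Annexin V-only cells look double-positive.

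At stake would be what the apoptosis and necrosis figures mean, and whether the group comparison treats all samples alike.

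**Working it through.** **Inputs.** The documents give no population shares, no between-subject spread, no sample size and no result for this assay, so there is no planned figure to reproduce. The only usable number is the 50,000-leukocyte count, and it applies here only if the cellular-immunity counting list covers this assay. The shares below are assumptions for illustration.

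**1. Effect of the label on one sample.** Let E, D and N be the shares of Annexin V-only, double-positive and PI-only cells.

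- Apoptosis is E or E + D; the difference is (E + D) − E = D.
- Necrosis is N or N + D; the difference is (N + D) − N = D.

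Assume E = 10% and N = 1%:

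| D | Apoptosis | Necrosis |
|---|---|---|
| 1% | 10% or 11% | 1% or 2% |
| 5% | 10% or 15% | 1% or 6% |

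This holds for relabelling a fixed quadrant. Moving the quadrant boundaries would change E, D and N themselves.

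**2. Comparison with counting error.** At 50,000 events, D of 1 to 5% is 500 to 2,500 events. The counting standard error of a 10% share is √(0.10 × 0.90 / 50,000) = 0.00134, or 0.134 percentage points. The shift is then 1/0.134 = 7.5 to 5/0.134 = 37.3 standard errors. That looks large, but 0.134 points is the counting noise within one tube. The Mann-Whitney test compares subjects, and its precision depends on the spread between them, which the documents do not give. The ratio therefore says nothing about whether a group comparison would change.

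**3. Effect on the group comparison.** Suppose one rule is used for every sample.

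- If D is the same in all samples, E + D is E plus a constant. Ranks, and hence the Mann-Whitney result, are identical.
- If D varies between subjects, E and E + D are different variables. If the joint distribution of (E, D, N) is the same in both groups, so is the distribution of any fixed combination of them. The test keeps its level under either label.

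The label changes what is being compared, not whether the comparison is fair. Bias would need the rule to differ systematically between groups, and nothing in the documents suggests that. The choice of program does not imply it, because the same quadrants can be set in either.

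**4. Compensation: the sections side by side.**

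- The counting list is introduced for cell samples on the instrument, not for antibody panels alone.
- The headings of the oxygen-radical (ROS) and Annexin V/PI sections describe sample preparation. The ROS section has no counting step, and the Annexin V/PI section only says that counting follows. The list under *Investigation of cellular immunity indicators* is the only account of how counting is done.
- The unstained tube in the Annexin V/PI section fits the voltage step in that list.
- The preparation steps for the cellular-immunity panel name no unstained or single-stain tube either, yet the same section makes both controls compulsory. The document does not write compensation controls into preparation steps, so their absence here is not evidence that they were left out.

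The volumes do not alter this. Read as 100 µl per tube, the two tubes use the whole suspension (2 × 100 = 200 µl). Single-stain controls would then have to come from another preparation, which the text neither describes nor excludes.

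**The case for a change.** The best case for acting is that a reader cannot tell from the document what apoptosis and necrosis mean in this assay, that the two labels differ by exactly D whatever its value, and that a few sentences would settle both points. Part of this stands. The definitions are absent, the algebra is right, and an open choice gives an analyst some freedom that a written rule would remove.

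It does not show a flaw in the plan. No stated rule gives a wrong answer, and nothing limits the output to two numbers, so reporting three populations also fits the text. Nothing in the document makes this assay a primary endpoint or ties a decision to it. Population definitions are equally absent for the antibody panel and the ROS assay, which points to a brief document rather than a defect peculiar to this assay.

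Falling back on total Annexin V-positive cells would not be a clear gain. The identity E(1 − m) + (D + E·m) = E + D shows that the total is unaffected when a fraction m of Annexin V-only cells is misread as double-positive. It covers spill-over in that direction only, and the total gives no value for necrosis.

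**Conclusion.** No change to the plan is needed. The missing quadrant definitions are a gap that analysts fill sensibly with a conventional scheme, and they would name that scheme when reporting results. The compensation doubt is largely answered by the compulsory counting list, which is worded for cell samples generally.

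The label can move each readout by D in a single sample: 1 to 5 points under the assumed shares, unknown in fact. No effect on the Mann-Whitney comparison can be shown from the documents. This conclusion assumes that one set of quadrants was applied to all samples in whichever program was used, and that the counting list, including single-stain compensation, was followed for this assay. The text is compatible with both assumptions but confirms neither outright. Evidence that the rule differed between the groups would reopen the question.
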